6.3.3.2 Determine statistical precision of estimates for individual pathogen prevalence

The large number of cases will allow for a very high degree of power for detecting novel pathogens and for precision around the estimates of all pathogens.

All PERCH sites are expected to have >85% power to detect pathogens with prevalences of 5-10% with precision ± 5%. Larger sites will provide high power for stratified analyses (i.e., for determining if etiology differs by severity of disease, or by HIV status). Pooled analyses will provide high power to detect rare and novel pathogens and will enable us to conduct and explore many small sub-group analyses while adjusting for age, site, and season/year.

Prevalence of pathogen: 10.0%

Figure VIII. Power to detect pathogens with 5%, 8% and 10% prevalence, ruling out lower bounds of 0%, 3%, and 5%, respectively, for varying N (range 300 cases to 1200 cases), for 2-sided alpha=0.01.

Cases and controls will be used to evaluate the epidemiological risk factors for pneumonia and to estimate risk factors for significant etiological sub-groups of pneumonia (e.g. pneumococcal pneumonia, RSV, tuberculous pneumonia, etc.). For detecting ORs≥2.0, refer to the power calculations for 6.4.2.1 above.

Version 6.0_15Nov2013

Illustration: Vitamin D has recently been shown to be an important risk factor for morbidity in persons of all ages. To assess if it is also an important contributor to development of pneumonia in young children, the proportion deficient in Vitamin D will be compared between cases and controls. If prevalence of Vitamin D deficiency is 30% or more in the cases, we have over 95% power to detect an $OR \ge 2.0$ at each of the sites.

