hospitalised PTB in children presented as acute pneumonia with less than 10 days of symptoms. (Jeena, Pillay et al. 2002) Additionally, other studies in Africa have identified MTB in 8-15% of children hospitalised with acute community-acquired pneumonia, irrespective of HIV infection status (Madhi, Petersen et al. 2000; Zar, Apolles et al. 2001; McNally, Jeena et al. 2007). The latter studies may under-estimate the role of MTB in the etiology of severe childhood pneumonia, as these studies generally used induced sputum or gastric washings, which only has a sensitivity of 23-30% for diagnosing PTB. The use of lung aspiration as a diagnostic procedure is expected to enhance our ability to detect pediatric cases of TB, as it has with adults (Scott, Hall et al. 2000). The role of non-tuberculous mycobacterial infections in the etiology of childhood pneumonia remains to be established. Although the burden of non-tuberculous mycobacterial disease is linked to the prevalence of HIV infection among children, diagnosis is essential for the proper management of affected patients. Furthermore, an unbiased approach to diagnostic sampling is the only way to discover new associations between pathogens and clinical pneumonia.

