- 2. Risk factors for infection with a given pathogen, including among other variables age, vaccination status, socioeconomic status, nutritional status, HIV infection, and antibiotic use are allowed to affect the risk of having each of the 30+1 infections. Some of these risk factors may also affect the general probability of developing 'hospitalized pneumonia' by a pathway other than the specific infection, for example, by reducing access to medical care.
- 3. Hospitalized, severe pneumonia is caused by one or more of the 30+1 pathogens causing infection and possibly by two-way interactions between them.
- We do not directly observe the presence of each infection. Rather the presence of infection by each pathogen must be inferred from up to 40 laboratory test results ("M") (illustrated in Table XII).

Table XII. Determination of infection status for30 pathogens using results from 40 lab tests						
Path 1 Path 2 Path 30						
Lab test 1	infected	NA	NA			
Lab test 2	NA	infected				
Lab test 40	Infected	Infected	NA			

5. The sensitivity and specificity of each laboratory test will be represented by a distribution on (0,1) (i.e., estimates of sensitivity and specificity can range from >0% up to and including 100%). Information from existing literature on the laboratory assays will be used to estimate their sensitivity and specificity. Uncertainty bounds around the sensitivity and specificity measures of the lab tests will be incorporated.

Data analysis ignoring measurement error. If the infection status for each of the 30 pathogens was known for each pneumonia case and for controls, the approach to analysis would have two parts, denoted A, in red, and B, in green, in Figure 6 below.

Figure VIII. Analysis approach

In Part A, among the cases and among the controls we will regress the presence/absence of infection for each pathogen on risk factors. The co-occurrence of infections would be of particular interest. We will therefore estimate the pairwise odds ratio for each of the 30 choose 2 = 435 pairs of infections, focusing on a smaller subset (e.g. top 30) with substantial prevalence. *Using marginal models* (e.g. Diggle, Heagerty, Liang and Zeger, 2002), the odds ratios could be regressed on covariates to build an understanding of what factors (e.g. age, nutritional status, vaccination status) influence the co-occurrence of pairs of infections (Diggle PJ 2002).

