Measurement error: The main challenge is that infection status will not be observed exactly for any child. Rather a series of laboratory test results will provide noisy evidence about each infection. For each test, there will be some degree of prior knowledge about its sensitivity and specificity. *A measurement error model* will be included in the analysis as represented by Part C in Figure 6 above.

We will consider two approaches for incorporating measurement error. In the first we will assume that the lab test results are independent of one another. We will use the external knowledge about sensitivity and specificity to set prior distributions for each. The joint probability distribution of the unknown infection status of a child will be inferred from the test results given the child's values of X and Y. We will only infer the univariate and bivariate marginal distributions. It will be possible to infer the class probabilities in the latent class version.

This approach ignores the likely correlation among test results that use the same body fluid or extraction process. We will extend the independence model by allowing for fluid and extraction "errors" that cause all of their test results to be corrupted (usually toward zero).

Approach to analysis: Once the measurement error is acknowledged, analysis will be implemented *using a Bayesian hierarchical model and Markov chain Monte Carlo (MCMC) methods of inference*. We will repeatedly simulate from the conditional distributions of the infection statuses (I) and the model parameters given the observable (X, Y, M). The histograms that are the target of inference will be constructed, with uncertainty, by summarizing the distribution of the I's and of the I's from the analysis. In the first months of the project, the detailed specification of the hierarchical model will be developed and tested on simulated data.

6.2.2 Estimate the fraction of pneumonia attributable to pathogens for which vaccines are currently under development

(See section 6.2.1. above).

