6.3.3 Power

Key analyses addressed in this section include determining:

- i. the association of pneumonia with detection of pathogens in nasopharyngeal specimens
- ii. the statistical precision of estimates for individual pathogen prevalence
- iii. the risk factors associated with pneumonia
- iv. the background prevalence of risk factors in the study population

Case-control analyses will be used to address (i) and (iii), and case-series analyses will be used to address (ii) and (iv).

For case-control analyses, an equal number of cases and controls is assumed. Analyses will be conducted both by site and pooled across sites. Site-specific and between-site analyses will illuminate which etiologies are common globally and which vary in importance depending on geography and local epidemiologic settings.

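### The site-level power and ±5-point precision in section 6.3.3.2 hold for raw test positivity, not for the sensitivity-corrected prevalence of M. tuberculosis that section 6.2.1 sets out to estimate

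*Protocol*

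**What the plan says.** Section 6.3.3.2 promises a large number of cases "for precision around the estimates of all pathogens" and then states that "All PERCH sites are expected to have >85% power to detect pathogens with prevalences of 5-10% with precision ± 5" (percentage points). The figure caption gives the whole basis of the calculation: prevalences of 5%, 8% and 10%, "ruling out lower bounds of 0%, 3%, and 5%, respectively, for varying N (range 300 cases to 1200 cases), for 2-sided alpha=0.01". Section 6.3.3 classes this as a case-series analysis, so it is a one-sample calculation on cases. Neither sensitivity nor specificity appears among the inputs.

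Section 6.2.1 describes the analysis itself. Its premise is that "The main challenge is that infection status will not be observed exactly for any child". Each laboratory test is given a distribution for its sensitivity and specificity, that uncertainty is carried forward, and a Bayesian measurement-error model yields the prevalence of infection and the frequency of each pathogen as a cause.

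Section 1.1.2, discussing earlier African studies of M. tuberculosis, says they generally used induced sputum or gastric washings, "which only has a sensitivity of 23-30% for diagnosing PTB". M. tuberculosis is named in the second primary objective (section 2.1).

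**The concern.** The power section and the analysis section appear to concern different quantities. If a test finds only a fraction Se of infected children, n cases yield about n × prevalence × Se positives. Converting positivity back to prevalence then multiplies the standard error by 1/Se. A site that can separate 10% from 5% positivity with high power may be unable to separate 10% from 5% infection.

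This matters because sections 6.3 and 6.3.1 justify the case numbers by the ability of each of the seven sites to describe its own etiology with reasonable precision. The sentence in 6.3.3.2 offers that assurance for every site and every pathogen. For a pathogen in the primary objectives, the protocol's own sensitivity figure contradicts it.

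**Working it through.** **Inputs from the protocol.** Contrasts 10% vs 5%, 8% vs 3% and 5% vs 0%; two-sided alpha 0.01, so z = 2.576 (figure caption, 6.3.3.2). Site targets: Thailand 500; Bamako and Basse 700; Lusaka 800; Soweto, Dhaka and Kilifi 1200. The low scenario is 70% of target, which is 350 for Thailand (Table XV). TB sensitivity Se = 0.23 to 0.30 (1.1.2).

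**Assumptions, both favourable to the protocol.** Specificity is 100% (the protocol gives no value) and Se is known exactly.

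**Step 1: reproduce the stated figure.** Score form:

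power = Φ[(p1 − p0 − z√(p0(1−p0)/n)) / √(p1(1−p1)/n)]

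For 10% vs 5%, n = 500: √(0.05×0.95/500) = 0.00975 and √(0.10×0.90/500) = 0.01342. So Φ[(0.05 − 2.576×0.00975)/0.01342] = Φ(1.86) = 96.8%. The Wald form gives Φ(0.05/0.01342 − 2.576) = Φ(1.15) = 87.5%, and the exact binomial 96.1%. At n = 350 the score form gives 89.4%, the exact 83.6% and the Wald 70.6%. For 8% vs 3% the score form gives 99.4% at n = 500. The claim of more than 85% therefore reproduces at the site targets with no sensitivity or specificity term.

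**Step 2: the same test on infection prevalence.** With specificity 100%, observed positivity is Se × prevalence, so p1 and p0 are each multiplied by Se.

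n = 500, Se = 0.23: p1 = 0.0230, p0 = 0.0115. Φ[(0.0115 − 2.576×0.00477)/0.00670] = Φ(−0.12) = 45%.

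n = 500, Se = 0.30: p1 = 0.030, p0 = 0.015. Φ[(0.015 − 2.576×0.00544)/0.00763] = Φ(0.13) = 55%.

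| Cases | 10% vs 5%, Se 0.23 to 0.30 | 8% vs 3%, Se 0.23 to 0.30 |
|---|---|---|
| 350 | 35 to 43% | 51 to 60% |
| 500 | 45 to 55% | 63 to 73% |
| 700 | 58 to 69% | 75 to 84% |
| 800 | 63 to 74% | 80 to 88% |
| 1200 | 80 to 89% | 92 to 97% |

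For 10% vs 5%, 85% power needs 305 cases with a perfect test, 1067 with Se 0.30 and 1399 with Se 0.23. Put the other way, 500 cases reach 85% only if Se is at least about 0.63.

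**Step 3: interval width.** Half-width of corrected prevalence = z√(q(1−q)/n)/Se, with q = Se × prevalence. At true prevalence 10% and n = 500:

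- 99%: 2.576×0.00670/0.23 = ±7.5 points; 2.576×0.00763/0.30 = ±6.6 points.
- 95%: 1.96×0.00670/0.23 = ±5.7 points; 1.96×0.00763/0.30 = ±5.0 points.
- A perfect test gives ±3.5 (99%) and ±2.6 (95%).

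Scaling the 99% values by √(500/n) gives about ±5.5 to ±6.3 at n = 700 and ±4.2 to ±4.8 at n = 1200, so the three largest sites keep the ±5.

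**Step 4: what survives.** For 5% vs 0%, the chance of at least one positive at n = 500 and Se 0.23 is 1 − (1 − 0.0115)^500 = 99.7%, if specificity is 100%. Pooled over 6300 cases, power is above 99.9% even at Se 0.23.

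**The case against.** The strongest reply is that this part of the protocol uses prevalence to mean detection. Section 6.3.3.1 defines its proportions as specimens in which the pathogen is detected and calls the comparison a first step. Read that way, the arithmetic in 6.3.3.2 is correct, and that part of the reply stands. But 6.3.3.2 does not say it means positivity, and section 6.1 sets the target as prevalence of infection. Under that reading the precision also fails once corrected: for observed positivity of 5-10% at 500 cases, the 99% half-width of corrected prevalence is about ±8 to ±15 points.

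A second reply is that several specimens raise combined sensitivity. This helps only in part. A second induced sputum is taken at some sites (4.5.1.5). Lung aspirates are planned at four sites, not including Thailand, and only a minority of cases are amenable (4.2.4). An assumed combined sensitivity of 0.50 still gives about 76% at 500 cases for 10% vs 5%.

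A third reply is that operating characteristics of a model still being specified belong in later documents. That is fair for the model. It does not cover a stated figure that the protocol applies to all sites and all pathogens.

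Three stronger readings might be inferred, and the documents do not support them:

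- That the claim fails for imperfectly tested pathogens in general, including those found by nasopharyngeal PCR. TB is the only pathogen for which the protocol states a test sensitivity. Figures for PCR after subtracting control positivity would need a sensitivity and a background rate that it does not give.
- That small sites would miss TB altogether, or that a low count would be read as absence. Simple detection survives, section 1.1.5 says failure to identify a pathogen does not rule it out, and 6.2.1 carries test uncertainty into the reported estimates.
- That only the pooled estimate should be reported. That would discard the site-specific estimates that the protocol plans.

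**Conclusion.** The concern holds in a limited form. The more-than-85% power and ±5-point precision describe observed test positivity, while the analysis targets corrected infection prevalence. For M. tuberculosis at the protocol's own 23-30% sensitivity, power for 10% vs 5% is below 85% at every site of 800 cases or fewer. At the 1200-case sites it is 80% (Se 0.23) to 89% (Se 0.30). The ±5-point precision at 10% prevalence is missed at 500 cases at the 99% level that matches the stated alpha, and is borderline at 95%.

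These figures use the score form, specificity 100% and known sensitivity. Prior uncertainty in either test property would widen the intervals. The perfect-test basis is inferred from the caption's inputs and from the reproduction; the protocol does not state it. 10% vs 5% is the hardest of the three contrasts. For 8% vs 3%, the 1200-case sites keep 92-97%, and 800 cases give 80-88%.

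**What to change.** In section 6.3.3.2:

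1. State that the more-than-85% power and ±5-point precision refer to observed test positivity, and limit the wording on all sites and all pathogens accordingly.
2. Add power and interval width for sensitivity-corrected prevalence at each site size, over a stated range of sensitivity and specificity that includes 23-30% sensitivity for M. tuberculosis. The simulated-data testing already planned in section 6.2.1 can supply these.
3. Keep the site-specific estimates and report them with their wider intervals alongside the pooled estimate.

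The cost is some wording and an addition to planned simulation work. No sample size changes. The downside is that a stated figure becomes less favourable.

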6.3.3.4 Determine background prevalence of risk factors in the study population

The community prevalence of risk factors will be used to characterize the study population, to interpret differences in the etiologic distribution of pneumonia cases between sites, and to extrapolate the study findings globally. Refer to the power calculations for 6.4.2.2 above.

7 Data collection, management and monitoring

7.1 Overview of data management system

Each site participating in the PERCH trial will be responsible for developing and maintaining a data management system for the purpose of data entry, cleaning and storage. The DCC will be the central data repository for all sites participating in the trial. The DCC's goal is to maintain the integrity of the data and to ensure that they are as accurate as possible. The DCC will perform a secondary study database clean-up working closely with the participating sites to ensure that all collected data has been received and that all quality control checks were performed.

The DCC will develop a standard data definition table (DDT) which will be used to consolidate all sites data into a consistent format for storage in the central database. The DCC will maintain a specimen tracking process and link them to clinical data. The DCC will work closely with data managers from the sites to assure proper quality control checks are performed at the site level based on the central data editing plan. Data integrity will be validated by producing standard reports and distributing to the sites on a routine basis. Data collected electronically or via CRFs will be transferred from the sites to the DCC using a secure FTP server or other means as deemed appropriate.

The DCC will provide, as needed, support for sites needing data management assistance including system setup, data collection, and data cleaning. Possible data systems to be used may include DataFax or InfoPath as a means of data collection. In addition the DCC may provide assistance in modifying or enhancing existing systems in use by the sites. The details of the data cleaning process will depend on the data system being used but will adhere to procedures defined in the standard data editing plan.

7.2 Data entry, error checking, cleaning

When possible, data editing will be performed in real time during data collection, while the subject is still present. In the event this is not possible, data entry and error checking will be completed within a timely manner to maximize the ability to resolve detected errors. Each site will be responsible for developing data entry error checking code, based on the standard data editing plan provided by the DCC. The sites will be responsible for following up, in a timely manner, on any queries produced by this code, to ensure the data are as complete and accurate as possible. On a predefined cycle, the sites will send updated data to the DCC. When the data are received, the DCC will run a second round of edit checks on the data.

7.3 Data sharing/access

PERCH will use an electronic data system developed by the EMMES corporation at six of seven sites (the Kenya site will maintain a site-specific data capture system). Each site will be responsible for uploading their data in an agreed upon format and will only have access to their data. Study leadership and DCC personnel will be given access to data from all sites. The DCC will then retrieve and merge all site data into one master database for centralized storage, cleaning and analysis.

Results from the multiplex respiratory PCR panel (identified by numeric study ID only) will be made available to the Azure PCR company and the Fast-track Diagnostics company for the purposes of validating software that will be used in our study to automate the interpretation of PCR results. The process will be overseen by [name], chair of the PERCH laboratory working group.

All sites will maintain 'ownership' of the data that is generated locally, and would not be restricted from using/reporting these data in accordance with the PERCH publications policy (see Appendix A).

7.4 QA/QC procedures

Prior to enrollment of the first subject at each site a complete test of the data management system will be performed by each site in coordination with the DCC. The DCC will provide standard test data which will be entered and processed at each site. The sites will verify that error checking is compliant with the data editing plan through use of a checklist provided by the DCC. When the data entry is completed, the sites will export the test data in a predefined format, and transfer them to the DCC where the data will be validated to make sure it matches the original test data.

During the first few months of the study the DCC will frequently review the data for quality control (QC) to identify trends and other peculiarities in the data. Once a threshold has been reached, a regular schedule will be established for these QC procedures. Data that have been accepted into the central database will be reviewed with a more advanced set of data quality checks. Any discrepancies (i.e. missing forms or failed univariate or multivariate checks) that are discovered during the verification process will be flagged with quality control notes for clinical site clarification.

The data management system developed by the DCC in consultation with the PERCH study group will produce the following data quality assurance reports:

- Queries
- Missing forms
- Center performance
- Monitoring site work flow
- Follow-up visit schedules

This combination of reports will allow the sites, the DCC and the study leadership to monitor the quality of the data. In addition, they will provide the tools necessary to identify if the site may be falling behind with the submission of their data and corrections.

The DCC data management staff will work closely with the staff at the sites to help them understand the problems that the data quality assurance reports detect and to assist them with resolution. The DCC data management staff, with guidance from the study leadership, will serve as a first-line resource to the participating sites on how to complete the study forms accurately.

7.5 Data Security

The DCC has a commitment to maintain data security and subject privacy. Standard DCC practices and policies for the conduct of clinical research studies will be implemented and reviewed periodically. The DCC Director is responsible for assuring all CSPCC data security policies are enforced within the DCC. Employees are responsible for following all data security policies when conducting study work. All study data collected will be handled, maintained and stored at the DCC according to DCC standard practices and policies. The central database will be stored on a server behind the firewall provided by the Department of Veterans Affairs, in compliance with their data security standards.

Each site participating in the PERCH trial will be responsible for maintaining data security as defined by local procedures and minimum requirements provided by the DCC. These minimum requirements include:

- Access to rooms housing computers or systems containing study data must be restricted to authorized personnel
- Network access to study data must be restricted to study personnel
- Computers that contain or have access to study data and have access to the Internet must be protected by firewalls as appropriate
- Study data stored on laptops or other portable devices must be encrypted
- Computers used by study personnel must maintain current anti-malware protection as appropriate

Data transferred between sites and the DCC will be performed over secure file transfer protocol (SFTP) or other secure encrypted channel as appropriate.

